8. SAFETY

All CRF data will be listed by subject and chronologically by assessment time points. This will include rechecks, unscheduled assessments, and early termination.

Applicable continuous variables will be summarized using number of subjects (n), number and percent of subjects with missing data, arithmetic mean, standard deviation (SD), minimum, median, and maximum.

The level of precision will be presented as follows: minimum/maximum in the same precision as in the database, mean/median in one more precision level than minimum/maximum, SD in one more precision level than mean/median, and n and percentage will be presented as an integer.

Where individual data points are missing because of dropouts or other reasons, the data will be summarized based on reduced denominators.

Screen failure subjects will be listed.

8.1 Disposition of Subjects

Subjects will be summarized by number of subjects screened, enrolled, exposed to NP 1.0, randomized, completed, and discontinued the study with discontinuation reasons. Individual subject product use status (i.e., which products were administered to each subject) will also be provided along with their study completion status and date of study completion or discontinuation. The number of subjects administrated for each study product will also be presented.

8.2 Demographics

Descriptive statistics will be calculated overall for continuous variables (age, weight, height, and body mass index [BMI]) and further stratified by sex.

Frequency counts will be provided for categorical variables (race, ethnicity, and sex) overall and further stratified by sex.

Demographics will be summarized for the SAF and PK population.

8.3 Tobacco/Nicotine-Containing Product Use History Questionnaire

At the Screening Visit, subjects will be asked questions about their tobacco-and/or nicotine-containing products use history. The questions will capture frequency and quantity of tobacco and/or nicotine-containing product use over the past 4 weeks, number of continuous years of cigarette smoking, and intention to quit using tobacco and/or nicotine products within the next 3 months.

Descriptive statistics will be calculated for continuous variables overall and further stratified by sex. Frequency counts will be provided for categorical variables overall and further stratified by sex. The analysis will be for the SAF and PK population.

8.4 Fagerström Test for Nicotine Dependence (FTND)

Level of nicotine dependence will be assessed using the FTND in its revised version [7] as updated in 2012 [8].

The questionnaire consists of six questions. The scores obtained on the test permit the classification of nicotine dependence into three levels: Mild (0 to 3 points); Moderate (4 to 6 points); Severe (7-10 points) [8].

Descriptive statistics (including number of subjects (n), number and percent of subjects with missing data, median, first and third quartiles, and minimum and maximum) will be calculated for FTND score overall and further stratified by sex. In addition, frequency counts will be provided for nicotine dependence levels (mild, moderate, and severe) and further stratified by sex. The analysis will be for the SAF and PK population.

8.5 Medical History

All Medical Histories and Concomitant Diseases will be coded using the Medical Dictionary for Regulatory Activities (MedDRA®), using the version specified in the DMP and listed by subject.

8.6 Adverse Events

All AEs occurring during this clinical trial will be coded using MedDRA® using the version specified in the DMP.

All AEs captured in the database will be listed in by subject data listings including verbatim term, coded term, product, severity, relationship to study product, and action taken; All adverse events will be summarized. Adverse events that occur after ICF and prior to the product test on Day -1 and those that occur during the safety follow up (FU) period (after discharge to safety FU visit) will be summarized separately under admission/safety FU period.

A study product use-emergent adverse event is defined as an AE that is starting or worsening at the time of or after study product administration. An AE that occurs during the washout period between study products is considered study product use emergent to the last study product given.

If the onset time of an AE is missing and the onset date is the same as the product administration date, the AE will be considered product use-emergent to the prior and current product. If the onset time of an AE is missing and the onset date does not fall on a product administration date, the AE will be considered product use-emergent for the last product administered. If the onset date of an AE is missing, the AE will be considered product use-emergent and attributed to each product on the study, unless the onset date is known to have occurred within or between specific product periods.

All PUEAEs will be summarized by product and overall. The number and percentage of subjects with AEs, SAEs (including deaths), and product events listed will be tabulated by

Statistical Analysis Plan Number CA36095

system organ class and preferred term. Summaries will also be presented for AEs leading to product discontinuation, AEs leading to study discontinuation, AEs by relatedness to product exposure (including expectedness) and relatedness to study procedures, AEs by severity, and AE by action taken related to the product. Tabulations will be performed for both the number of subjects experiencing an event and the number of events.

SAEs, if present, will also be listed. Applicable narratives will be included in the CSR.

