8.7 Clinical Laboratory Tests (Clinical Chemistry, Hematology, Urinalysis)

Clinical laboratory evaluations (clinical chemistry, hematology, and urinalysis) will be performed at Screening, Admission (Day -1), and at Discharge (Day 3), or an early termination assessment will be performed, as applicable.

Out-of-range values and corresponding recheck results will be listed. Other lab results within this panel and time point will also be listed.

For all numeric laboratory values, descriptive statistics will be presented for each laboratory test by study day. Change from baseline will be summarized in a similar manner. Baseline is defined as the result closest and prior to the first product administration, which may include unscheduled or recheck results. This will typically be the result collected on Admission (Day -1). Post product use unscheduled events or rechecks will not be included in summaries. Similarly, early termination results will not be included in summaries.

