8.8 Vital Signs

Vital signs (systolic and diastolic blood pressure, pulse rate, and respiratory rate) will be measured at Screening, Admission (Day -1), Day 1 to Day 3 prior to T_{0M}. If applicable, an early termination assessment will be performed.

All parameters will be recorded in supine position after the subject has rested for at least 5 minutes. Subjects should have abstained from using any nicotine/tobacco containing products for at least 15 minutes prior to the assessment.

For those results outside of the normal range, the Investigator will determine appropriate follow-up including reporting of any AEs.

Descriptive statistics will be reported for vital signs measurements (blood pressure, pulse, respiratory rate) by study day. Change from baseline will be summarized in a similar manner. Baseline is defined as the result closest and prior to the first product administration, which may include unscheduled or recheck results. This will typically be the result collected prior to T_{0M} on Day 1. Post product use unscheduled events or rechecks will not be included in summaries. Similarly, early termination results will not be included in summaries.

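### SAP 8.6 most naturally places adverse events after the Day -1 product test under NP-1, but the SAP never says whether that test is a product administration

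*SAP*

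**What the plan says.** SAP 8.6 builds the AE tables in three steps.

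1. It carves out two groups: "Adverse events that occur after ICF and prior to the product test on Day -1", and events in safety follow-up. Both "will be summarized separately under admission/safety FU period".
2. It calls an AE product use-emergent if it starts or worsens at or after study product administration, a term it does not define. It then adds that "An AE that occurs during the washout period between study products is considered study product use emergent to the last study product given".
3. It states that "All PUEAEs will be summarized by product and overall". It also says more broadly that "All adverse events will be summarized". It names no column or period for the product test.

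Other sections bear on the status of the test:

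- SAP 3.1 and Protocol 6.2.1: every enrolled subject uses one NP-1 pouch for 30 minutes on Day -1 and then abstains until the first Day 1 use.
- SAP 4.1.2 counts the test as exposure for the safety population, and Protocol 6.5.1 starts product dispensing on Day -1.
- SAP 3.1 and Protocol 6.2.2 place the three-day exposure period after the test, on Day 1 to Day 3.
- SAP 8.8, on vital signs: "Baseline is defined as the result closest and prior to the first product administration", and "This will typically be the result collected prior to T_{0M} on Day 1".

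**The concern.** The by-product tables are the place where AEs of the six products stand side by side. If events after the Day -1 test enter the NP-1 column, that column covers more product use than the other five. The extra use is not randomised and always comes first. NP-1 could then look less well tolerated for reasons of bookkeeping alone.

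If the test is not an administration, its AEs are not product use-emergent, yet they also fall outside the admission and follow-up group. SAP 8.6 then defines no place for them in the tables by product or period. Protocol 2.1.2 says that NP 1.0 has not been tested in humans, so AEs at first use are ones a reader will want to find easily.

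**Working it through.** The plan gives no AE rate and no figure on this point, so there is nothing to reproduce. The check is a reading of the text, followed by an illustration of size.

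**Where a test AE goes under SAP 8.6.** The early carve-out ends at the test, so an AE with onset after the test and before the first Day 1 use is outside it. NP-1 is a listed study product and the last one given, because subjects abstain until Day 1. If the test counts as an administration, the AE is emergent to NP-1 and enters the NP-1 column.

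**What SAP 8.8 implies.** Table 5 in Protocol 9.2 puts Day -1 vital signs before enrolment and the test after it, so a pre-test value exists. If the test were the first administration, the baseline would typically be that Day -1 value. SAP 8.8 names the Day 1 pre-T0M value instead, which fits its definition only if the test is not an administration. SAP 8.7 and 8.9 do not help: laboratory tests and ECG are scheduled on Day -1 before the test and next on Day 3, so a Day -1 baseline fits either reading.

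**Use count, if the test is an administration.** SAP 3.1 has six product use periods and six products, so a completer uses each product once on Day 1-3. With the planned 24 subjects all completing, NP-1 has 24 × 2 = 48 uses and each other product has 24.

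**Share of subjects with an AE (illustration).** Assume a per-use AE risk p equal for all products, and a correlation rho between a subject's two NP-1 uses. Take randomised completers only.

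- P2 = P(at least one AE in two uses) = 1 − [(1−p)² + rho·p(1−p)]
- Ratio to one use: P2/p = 1 + (1−p)(1−rho)

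| p | rho = 0 | rho = 0.5 | rho = 0.8 |
|---|---|---|---|
| 5% | 1.95 | 1.48 | 1.19 |
| 10% | 1.90 | 1.45 | 1.18 |
| 20% | 1.80 | 1.40 | 1.16 |
| 30% | 1.70 | 1.35 | 1.14 |
| 40% | 1.60 | 1.30 | 1.12 |

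At p = 10%, each other product would show 24 × 0.10 = 2.4 subjects on average. NP-1 would show 24 × 0.19 = 4.56 (rho = 0), 24 × 0.145 = 3.48 (rho = 0.5) or 24 × 0.118 = 2.83 (rho = 0.8).

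**Unequal risk at the test use.** Let the test-use risk be k·p, with p = 10%.

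- rho = 0: P2 = 1 − (1−kp)(1−p). For k = 0.5, P2 = 1 − 0.95 × 0.90 = 0.145, ratio 1.45. For k = 1.5, P2 = 1 − 0.85 × 0.90 = 0.235, ratio 2.35.
- k = 0.5, rho = 0.5: joint risk = 0.05 × 0.10 + 0.5 × √(0.05 × 0.95 × 0.10 × 0.90) = 0.0377. P2 = 0.05 + 0.10 − 0.0377 = 0.112, ratio 1.12.
- k = 0.5 at the largest feasible rho: the joint risk cannot exceed 0.05, so rho ≤ (0.05 − 0.005)/0.0654 = 0.69. There P2 = 0.10, ratio 1.0.

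**Test-only subjects.** Alternates and subjects who stop after the test may enter the NP-1 denominator, while their post-discharge AEs go to the follow-up summary. Their net effect cannot be determined from the documents.

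**The case against.** The strongest reply is that the NP-1 attribution is an inference. The rule on washout AEs speaks of the interval between study products, which could mean randomised products only, and the documents separate the Day -1 test from the exposure period. This stands: a reader might infer that SAP 8.6 definitely assigns test AEs to NP-1, and the documents do not support so firm a statement. The reply does not remove the gap, however, because the alternative leaves those AEs without a column.

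The SAP is to be supplemented by table shells (SAP 1), which were not supplied and may already include a test column. That also stands, although the SAP text holds the attribution rule and is silent on this.

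There are partial safeguards. Protocol 12.7 also reports exposure-period safety data by sequence, and SAP 8.1 presents the number of subjects given each product. Both help a reader see what lies behind the NP-1 column, but neither separates test AEs by product.

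On size, a low test-use risk among randomised subjects is plausible, since those unwilling or not ready after the test are discontinued. The inflation could then vanish. This is accepted.

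Finally, taking test AEs out of the NP-1 column lowers the displayed counts for a new product. That is a fair objection to a bare removal and calls for a visible cross-reference.

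**Conclusion.** The point holds as a minor one. On its most natural reading SAP 8.6 places test AEs under NP-1, while SAP 8.8 and the Day 1-3 exposure period imply that the test is not an administration. The SAP has to choose.

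Only the two-to-one use count comes from the design. It is conditional on the first reading and on completion of all six uses. The inflation in subjects with an AE rests on assumed p, rho and test-use risk; in the cases worked it runs from none (1.0) to 2.35. A reader might infer from the rho = 0 column that NP-1 incidence will be nearly doubled; the documents give no AE rate or correlation that would support this.

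Nor would test AEs be lost on the second reading, since all AEs are still listed and are to be summarised. The effect is confined to descriptive safety tables. PK results do not change, and Day 1-3 events can be recovered from the listings.

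**What to change.** - In SAP 8.6, state whether the Day -1 product test is a study product administration, and make the baseline wording in SAP 8.8 agree with it.
- Show AEs with onset from the test to the first randomised use (or to discharge for test-only subjects) in a separate NP-1 product test column, with all tested subjects as denominator.
- Restrict the six product columns to Day 1-3 uses, each with the subjects given that product on those days as denominator. Keep every event in the overall column.
- Add a footnote to the NP-1 column that points to the test column, because its displayed counts will be lower.
- Check the table shells for consistency.

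The cost is one or two SAP sentences, one extra table column and the footnote. No event is dropped and no study procedure changes.

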3.1 STUDY DESIGN

This is a single-center, randomized, controlled, open-label, cross-over study in healthy smoking subjects to investigate the nicotine PK profiles of 4 variants of NP 1.0 compared to marketed Velo-NP and Zyn-NP. In addition, PD effects will be evaluated to provide further insights on NP 1.0 product acceptance and abuse liability. The study will be conducted with 6 product use periods and 6 sequences in a Williams design (cross-over).

A Screening Visit will be conducted within 21 days (Day -22 to Day -2) prior to Admission (Day -1) to the investigational site (Figure 1). Subjects will be screened against eligibility criteria.

Statistical Analysis Plan Number CA36095

Figure 1 Study Design

Qualified subjects will return to the investigational site for Day -1. Subjects should have fasted for at least 10 hours prior to the safety laboratory assessments. After confirmation of eligibility, subjects will be enrolled. All subjects that are not enrolled will be considered as screen failures.

On Day -1, enrolled subjects will perform a product test using NP-1 for 30 minutes (\pm 1 minute). After the product test, subjects not willing and/or not ready to use NP 1.0 during the study will be discontinued from the study, will enter the 3-day Safety follow-up period, and will be replaced.

Subjects willing and ready to use NP 1.0, Velo-NP and Zyn-NP during the study after product test will start their exposure period of 3 days.

Twenty-four (24) subjects will be randomized to 1 of 6 possible sequences of product use on Day 1 to Day 3 with at least 25% of each sex (see Figure 1). The randomization process including the randomization sequences will be documented in the randomization plan.

On Day 1 to Day 3, after at least 8 hours of abstinence from any nicotine/tobacco containing products (nicotine wash-out), subjects will use one NP for 30 minutes (± 1 minute) according to randomized product use sequence in the morning and in the afternoon, by placing the NP between the upper lip and gum. Subjects will complete self-reported assessments of product evaluation, craving, liking, satisfaction, and intent to use again.

The start of the 30 minutes use period will be defined as T₀. T₀ in the morning (T_{0M}) and in the afternoon (T_{0A}) on Day 1 to Day 3 should be approximately at the same time, within a window of \pm 30 minutes. Venous blood samples will be obtained according to the standard operating procedures (SOPs) at the investigational site.

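### SAP 8.6's rules for AEs with an incomplete onset do not fit two products per day: a date-only AE has three candidate uses but is sent to two products, and a missing-date AE can be charged to products never used

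*SAP*

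**What the plan says.** SAP 8.6 defines an emergent AE as one that starts or worsens when a study product is administered or afterwards. For an AE between products it says: "An AE that occurs during the washout period between study products is considered study product use emergent to the last study product given". It then gives three rules for incomplete onset:

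- Time missing, date is a product date: "the AE will be considered product use-emergent to the prior and current product".
- Time missing, date is not a product date: "the AE will be considered product use-emergent for the last product administered".
- Date missing: "the AE will be considered product use-emergent and attributed to each product on the study", with an exception where the onset is known to lie within or between particular product periods.

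Emergent AEs are tabulated by product and overall. AEs before the product test, and AEs in the safety follow-up, have a separate line.

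SAP 3.1 describes a Williams cross-over with six sequences and six product use periods. On each of Days 1 to 3 a subject uses one pouch "according to randomized product use sequence in the morning and in the afternoon". The day before exposure also has a product: "On Day -1, enrolled subjects will perform a product test using NP-1 for 30 minutes".

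Protocol 12.7 assigns laboratory AEs found on Day 3 to the product of the previous day, in the singular.

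**The concern.** The date-only rule names two products, one prior and one current. With a single administration per date those two are all the candidates. With two administrations per date there is a third, and neither document says which of the day's two products is *current*. Two programmers could build different by-product AE tables from the same data, and each could omit the product last used before the event.

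The missing-date rule has a different fault. It does not depend on how many products are used per day, but it is not limited to products the subject received. The safety population (SAP 4.1.2) includes subjects exposed only at the product test, so the rule can charge an AE to products a subject never used.

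AEs are the basis of the safety assessment (protocol 12.7). With 24 randomized subjects, one subject with an event is 1/24 = 4.2 percentage points for a product, so the placement of a single AE is visible in the table.

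**Working it through.** **Two uses per day, confirmed from the plan's own figure.** Protocol 7.7.1 gives about 296 mL of blood for plasma nicotine at 4.0 mL per sample. SAP 6.1 gives 12 samples per use and 2 extra on Day 2.

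- Two uses per day: (3 × 2 × 12 + 2) × 4.0 = 74 × 4.0 = 296 mL, which reproduces the figure.
- One use per day: (3 × 1 × 12 + 2) × 4.0 = 38 × 4.0 = 152 mL, which does not.

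**Candidates for a date-only onset.** Until the morning use, the last product given is the final one of the previous product day. It is then the morning product, and later the afternoon product.

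| Date of AE | Uses that could be the last one given |
|---|---|
| Day 1 | NP-1 test, period 1, period 2 |
| Day 2 | period 2, period 3, period 4 |
| Day 3 | period 4, period 5, period 6 |

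On Days 2 and 3 these are always three different products. On Day 1 they reduce to two if NP-1 falls in period 1 or 2 and the test is tabulated under NP-1.

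**What a two-product reading omits.** The documents give no clock times, so this is an illustration only. Assume morning use at *t* = 07:00 to 10:00 and afternoon use *g* = 8.5 to 9 h later. The lower bound for *g* is 0.5 h of use plus the 8 h abstinence in protocol 6.6.1. Assume also that onset is uniform over 24 h.

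| Reading of *prior and current* | Omitted product | Share of the day | Range |
|---|---|---|---|
| previous afternoon and morning | afternoon | (24 − t − g)/24 | 5/24 = 21% to 8.5/24 = 35% |
| morning and afternoon | previous afternoon | t/24 | 7/24 = 29% to 10/24 = 42% |
| previous afternoon and afternoon | morning | g/24 | 8.5/24 = 35% to 9/24 = 38% |

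A rule naming all three omits none. These shares apply to date-only AEs on Days 1 to 3, not to AEs in general.

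**Missing date, period unknown.** There are six products. A subject who left after the NP-1 test would have the AE charged to 6 − 1 = 5 products never used. A subject who left after Day 1 has used NP-1 plus two period products. That leaves 6 − 3 = 3 never used, or 6 − 2 = 4 if one of the two was NP-1. An AE cannot start at or after administration of a product that was never administered, so the rule read literally conflicts with the definition in the same section.

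**Laboratory AEs.** Day 2 has two products (periods 3 and 4), so a single product of the previous day, as protocol 12.7 has it, is not defined.

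**The case against.** The strongest reply is that the date-only rule can be applied once per administration. On Day 2 that gives periods 2 and 3 for the morning use and periods 3 and 4 for the afternoon use, and the union is all three candidates. This reading is possible, but the SAP does not state it. It speaks of one administration date and one current product, and the reading ends at the rule proposed below.

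The second reply is that few AEs are involved. This stands. Protocol 8.2.1 has start dates and times recorded, subjects are confined and asked about AEs each day, and protocol 11.2.1 has missing data queried. The study is also exploratory, and every AE is listed by subject with its product, so an attribution can be checked.

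The third reply is that the missing-date rule has an exception for a known period and should be read with the emergent definition. The exception does narrow it. Where the period is unknown, though, the literal wording still covers all six products, and nothing says that the definition takes precedence.

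A reader might infer two stronger points, which the documents do not support:

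- *By-product AE counts in general are misassigned.* An AE with a recorded onset time goes to the last product given, which works with two uses a day.
- *Follow-up AEs are classified differently depending on whether a clock time was recorded.* The sentence that puts follow-up AEs on a separate line sets no condition on time, so timed and untimed AEs fall under it alike. The rule for dates without product use has no date to act on between products, since Day -1 and Days 1 to 3 all have product use. An idle rule misassigns nothing.

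**Conclusion.** The point holds for AEs with an incomplete onset, and only for those. For a known date with a missing time on Days 1 to 3, the SAP names two products where three uses are candidates, so attribution is ambiguous and can omit the product last used. For a missing date with an unknown period, the literal rule can charge three to five products that an early leaver never used.

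The number of affected AEs cannot be derived from the documents and is probably small. The 21% to 42% range rests on assumed clock times and uniform onset; it shows that the omitted part of the day is substantial under any two-product reading, and is not an AE error rate. The candidate list and the conflict with the emergent definition need no such assumptions. These are stated rules that misfit the design, and they are worth correcting because the correction is specific and nearly free.

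**What to change.** Amend SAP 8.6 so that the rules are defined by product use period:

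- **Date known, time missing, Days 1 to 3:** attribute the AE to every product that could have been the last one given on that date (last product of the previous product day, morning product, afternoon product), less any ruled out by recorded information.
- **Date missing:** attribute the AE only to products the subject actually used, keeping the existing exception for a known period.
- **Day 3 laboratory AEs (protocol 12.7):** state whether both Day 2 products or only the later one is meant. The SAP's rule for AEs between products points to the later one. The change can be recorded in SAP section 9, since protocol 12.1 allows changes to planned methods to be documented in the SAP and CSR.

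The cost is a few sentences and a few lines of attribution code, best settled before database lock. The small downside is that a date-only AE may be counted under three products instead of two; a footnote to the by-product table can say so.
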